Version and date of protocol: version 5, date: 07/18/2023

Study Protocol

Official Title: The effectiveness of chatbot facilitated education
on child and adolescent abuse for nurses

Protocol ID: IRB112-148-B

ClinicalTrails.gov ID: NCT06167031

Project PI : [name]

Project Co-PI : [name], [name]

Version/Date: version 5, 18/07/2023

Background

The incidence of child and adolescent abuse and neglect (CAN) is increasing both in Taiwan and globally. As frontline healthcare professionals, nurses play a pivotal role in the early identification and reporting of CAN. However, research indicates that insufficient knowledge and limited competency among nursing staff can impede timely recognition and notification of suspected cases. Strengthening nurses' knowledge and competencies in assessing and reporting CAN is therefore essential. With the advancement of technology, continuing nursing education has expanded beyond traditional lecture-based formats. In particular, online education has gained momentum since the COVID-19 pandemic, offering flexible, accessible learning opportunities. Chatbots, as a form of individualized digital learning, have emerged as a promising tool for enhancing nurses' ability to recognize and report CAN.

Objective

The study aims to evaluate the effectiveness of chatbot-facilitated education in assisting nursing personnel to prevent CAN. This evaluation will focus on the impact of this learning on CAN competency.

Method

An experimental study design was employed. Participants were purposively sampled and allocated to the experimental and control group. The experimental group received chatbot-facilitated education (CFE), while the control group received conventional lecture-based instruction. The course content, developed using the ADDIE instructional design model, comprised two modules: (1) Child and Adolescent Abuse and Neglect and (2) Nurses' Roles and Responsibilities in CAN. The *CAN Knowledge and Competency Scale* was used to measure learning outcomes at three time points: pre-intervention, one week post-intervention, and four weeks post-intervention.

Statistical Analysis Plan

The collected questionnaire data will be coded and analyzed using the SPSS for Mac version 29.0.1.0 statistical software package. The statistical analysis methods employed will include descriptive statistics and inferential statistics (Table 1-1). A significance level of $p < .05$ will be used for hypothesis testing.

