1. Descriptive Statistics

The central tendency and dispersion trends of the sample will be presented using frequency distribution, percentage, mean, and standard deviation to understand the distribution of the sample's basic attributes.

2. Inferential Statistics

(1) Chi-square test (χ^2 test)

- a. To test whether there are statistically significant differences in categorical variables between the two groups.

(2) Independent-samples t-test

- a. To test whether there are statistically significant differences in continuous variables between the two groups.
- b. To test whether the average scores of CAN intention to report, attitude toward reporting, and knowledge evaluations between the two groups are statistically significantly different.

(3) Paired-samples t-test

- a. To test whether there are statistically significant differences in CAN intention to report, attitude toward reporting, and knowledge evaluations within each group over three time points.

(4) Generalized Estimating Equation (GEE)

- a. To test whether there are statistically significant differences in CAN intention to report, attitude toward reporting, and knowledge evaluation scores between the two groups across different time points.

Table 1-1 Research hypotheses and analysis methods (1/2)

Research hypotheses	Assessment tool	Analysis methods	Statistical methods
1-1-1. There are differences in the intention to report CAN across three assessments within both the experimental and control groups.	CAN Knowledge and Competency Scale	IV: Different assessment time points DV: Scores for the intention to report CAN, attitude toward reporting CAN, and knowledge of CAN	Paired-sample t-test
2-1-1. There are differences in the attitude toward reporting CAN across three assessments within both the experimental and control groups.			
3-1-1. There are differences in the knowledge of CAN across three assessments within both the EG and CG.			
1-1-2. There are differences in the intention to report CAN across three assessments between the experimental and control groups.	CAN Knowledge and Competency Scale	IV: Group DV: Pre-test, post-test 1, and post-test 2 scores for the intention to report CAN, attitude toward reporting CAN, and knowledge of CAN	Independent-samples t-test
2-1-2. There are differences in the attitude toward reporting CAN across three assessments between the experimental and control groups.			

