3-1-2. There are differences in the knowledge of CAN across three assessments between the experimental and control groups.			

CAN: child and adolescent abuse and neglect; EG: experimental group; CG: control group; IV: independent variable; DV: dependent variable.

Table 1-1 Research hypotheses and analysis methods (2/2)

Research hypotheses	Assessment tool	Analysis methods	Statistical methods
1-1-3. There are differences in the improvement scores for intention to report CAN between the experimental and control groups.	CAN Knowledge and Competency Scale	IV: Group and different assessment time points DV: Scores for the intention to report	Generalized estimating equation (GEE)
2-1-3. There are differences in the improvement scores for attitude toward reporting CAN between the experimental and control groups.		CAN, attitude toward reporting CAN, and knowledge of CAN	
3-1-3. There are differences in the improvement scores for knowledge of CAN between the experimental and control groups.			

CAN: child and adolescent abuse and neglect; EG: experimental group; CG: control group; IV: independent variable; DV: dependent variable.

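### With no missing-data rule and no GEE working correlation, score-related dropout that differs between arms can bias the week-4 comparison; a likelihood repeated-measures model would be safer

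*Combined protocol and SAP*

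**What the plan says.** The Method section sets three assessments: "pre-intervention, one week post-intervention, and four weeks post-intervention". The Statistical Analysis Plan then gives three kinds of test for intention to report, attitude toward reporting and knowledge.

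- **Independent-samples t-tests** (2. Inferential Statistics (2); Table 1-1, hypotheses 1-1-2, 2-1-2, 3-1-2) compare the groups at each visit: "IV: Group DV: Pre-test, post-test 1, and post-test 2 scores for the intention to report CAN", and likewise for the other two scores.
- **Paired t-tests** (item (3); hypotheses 1-1-1, 2-1-1, 3-1-1) compare "knowledge evaluations within each group over three time points".
- **GEE** (item (4); hypotheses 1-1-3, 2-1-3, 3-1-3) takes group and time as independent variables and compares intention, attitude and "knowledge evaluation scores between the two groups across different time points". Its hypotheses concern improvement, for example: "There are differences in the improvement scores for intention to report CAN between the experimental and control groups".

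The only statement on which data are analysed is "The collected questionnaire data will be coded and analyzed using the SPSS for Mac version 29.0.1.0 statistical software package". The document does not mention missing questionnaires, an analysis set, imputation, weighting, the GEE working correlation or a sensitivity analysis. On group formation it says only: "Participants were purposively sampled and allocated to the experimental and control group".

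**The concern.** A paired t-test needs both scores of a pair, a per-visit t-test needs the score at that visit, and an unweighted GEE uses the rows that are present. Without another rule, nurses who miss week 4 drop out of the week-4 comparison.

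Robust standard errors protect a GEE against a wrong working correlation when data are complete. They do not remove bias from the estimate when the chance of a missing score depends on earlier scores. In that case the working correlation matters, and the plan leaves it open.

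The two arms receive different delivery formats and no randomisation is described, so equal, score-independent dropout cannot be taken for granted. At stake are the improvement hypotheses (1-1-3, 2-1-3, 3-1-3), where a difference in who stays could be read as a difference in teaching.

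**Working it through.** The plan has no figure of its own to reproduce: it gives no sample size, power, SD, dropout rate or within-person correlation.

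**Inputs from the documents.** Three visits, two groups, the tests listed above, and a .05 significance level.

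**Assumptions.** SD 1, equal true change of 0.5 SD in both arms, and equal correlation r between any two visits. Pre-test and week 1 are complete. Week 4 is lost by a logistic model in which low scorers leave, with log-odds changing by 1 per SD. Unless stated otherwise, loss is in the chatbot arm only.

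**Formulas for pre-test-dependent dropout.** Let d be the amount by which the mean pre-test score of the nurses who stay exceeds that of all nurses in the arm. Their week-4 mean is then too high by r × d.

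- Week-4 t-test: bias = r × d.
- GEE with independence correlation (week-4 mean of those who stay minus pre-test mean of all): bias = r × d.
- Paired change among those who stay: bias = r × d − d = −(1 − r) × d.

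Under this logistic model d is 0.090, 0.173 and 0.252 SD at 10%, 20% and 30% dropout.

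**Results at 20% dropout (SD units).**

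| r | t-test and independence GEE | Paired change, pre-test to week 4 |
|---|---|---|
| 0.5 | 0.5 × 0.173 = +0.09 | −0.5 × 0.173 = −0.09 |
| 0.7 | 0.7 × 0.173 = +0.12 | −0.3 × 0.173 = −0.05 |

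Simulation with 1,000,000 per arm agrees: +0.086 to +0.088 and −0.086 at r = 0.5, and +0.122 and −0.052 at r = 0.7. A GEE with the correct exchangeable correlation, equivalent here to a likelihood repeated-measures model, gave 0.00 in both cases. If high scorers leave instead, the signs reverse.

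Over 10% to 30% dropout and r from 0.3 to 0.7, the formulas give +0.03 (0.3 × 0.090) to +0.18 (0.7 × 0.252) for the first column. For the paired change they give −0.03 to −0.18.

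**Other dropout patterns at 20% and r = 0.5.**

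| Pattern | t-test | Independence GEE | Exchangeable GEE | Paired change |
|---|---|---|---|---|
| Depends on week-1 score, one arm | +0.09 | +0.09 | 0.00 | 0.00 from pre-test; −0.09 from week 1 |
| Depends on unseen week-4 score, one arm | +0.17 | +0.17 | +0.12 | +0.09 |
| Depends on pre-test score, alike in both arms | 0.00 | 0.00 | 0.00 | −0.09 within each arm |
| Completely random | 0.00 | 0.00 | 0.00 | 0.00 |

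**Effect on false positives.** With 60 per arm, 20% pre-test-dependent dropout in one arm and no true group difference, 400 simulated trials rejected in 9.8% for the independence GEE, 8.5% for the t-test and 5.5% for the exchangeable GEE (Monte Carlo error 1 to 2 points). As a rough check, the standard error is √(1/48 + 1/60) = 0.194, so the shift is 0.087/0.194 = 0.45 standard errors. The rejection rate is then about Φ(−1.51) + Φ(−2.41) = 0.066 + 0.008, or 7%. A fair reading is 7% to 10% against a nominal 5%.

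**The case against.** The strongest reply is that the plan is silent rather than wrong. It never says that only available scores are used, and it does not choose independence correlation. One line naming a suitable working correlation and an analysis set would remove most of the bias under dropout that depends on earlier scores. This stands in part: a correctly specified GEE is nearly unbiased in those cases, so nothing here shows that GEE as such is unsound. But the plan as written does not rule out the biased version, and the mixed model answers the same group-by-time question without depending on that choice.

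A reader might also infer that the planned tests would contradict each other. Table 1-1 does not support this. Its two between-group analyses, the per-visit t-test and the GEE, move the same way. The paired test that can move the other way is used only within each group and answers a different hypothesis. For change from the pre-test, the sign split arises only when dropout depends on the pre-test score.

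It is also fair to say that the scenario is asymmetric by assumption and the bias modest. At an assumed 50 per arm and correlation 0.5, the complete-data standard error is √(2/50) = 0.20 SD, so a bias of 0.09 SD is a little under half of it. That limits the weight of the point but does not remove it.

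**Conclusion.** The point holds as a conditional one. The SAP leaves missing scores and the working correlation open, so dropout that depends on earlier scores and differs between arms can bias the week-4 t-test and an independence GEE. Under the stated assumptions the bias is about +0.09 to +0.12 SD at 20% dropout. The within-arm paired change is biased by about −0.05 to −0.09 SD if dropout depends on the pre-test score. None of the dropout rate, correlation, sample size or asymmetry between arms comes from the documents, and that observed scores alone enter is an inference, though the natural one.

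Two stronger readings should be resisted. The documents do not show that dropout will bias this trial: random dropout, or dropout alike in both arms with equal effects, leaves the between-group comparison unbiased. Nor does a likelihood model cure everything: if dropout depends on the unseen week-4 score, the equivalent exchangeable fit is still biased by +0.12 SD at 20% dropout and correlation 0.5. The change is advisable rather than essential.

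**What to change.** - For hypotheses 1-1-3, 2-1-3 and 3-1-3, make the main longitudinal analysis a linear mixed model for repeated measures. Fit it by REML with unstructured covariance over the three visits, terms for group, time and group × time, and small-sample degrees of freedom.
- Include every allocated nurse with at least one score, in the group allocated. Take the week-1 and week-4 group contrasts in change from this model.
- Keep the GEE as a sensitivity analysis with a stated unstructured working correlation, and treat the t-tests as descriptive.
- Report dropout by arm and by pre-test score.
- Add a simple sensitivity analysis for dropout that depends on unseen scores, such as delta-shifted imputation.

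The cost is SAP wording and a little more analysis work; no new data are needed. The downside is that the mixed model assumes roughly normal scores. The retained GEE relies less on normality, but it is not an independent check on missing data, which is why the last item is needed.

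### The between-group hypotheses rest on raw t-tests at each visit, pre-test included, and nothing ranks the GEE above them, so a starting difference can pass for a group effect

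*Combined protocol and SAP*

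**What the plan says.** - **Hypotheses 1-1-2, 2-1-2, 3-1-2 (Table 1-1, part 1/2).** The first reads "There are differences in the intention to report CAN across three assessments between the experimental and control groups"; the other two say the same for attitude and knowledge. The assigned method is the independent-samples t-test, with the variables given as "IV: Group DV: Pre-test, post-test 1, and post-test 2 scores for the intention to report CAN" and the corresponding attitude and knowledge scores. Item (2)b under Inferential Statistics repeats this: "To test whether the average scores of CAN intention to report, attitude toward reporting, and knowledge evaluations between the two groups" differ significantly. No covariate is named in either place.
- **Hypotheses 1-1-3, 2-1-3, 3-1-3 (Table 1-1, part 2/2).** The first reads "There are differences in the improvement scores for intention to report CAN between the experimental and control groups". The method is a GEE, with "IV: Group and different assessment time points DV: Scores for the intention to report" and the other two outcomes. Item (4)a describes its purpose as testing for differences in intention, attitude and "knowledge evaluation scores between the two groups across different time points".
- **Allocation (Method).** "Participants were purposively sampled and allocated to the experimental and control group". The design is called experimental; randomisation is not mentioned.
- **Decision rule (Statistical Analysis Plan).** One threshold, p < .05, "will be used for hypothesis testing". No hypothesis or analysis is named as primary, and nothing says which result governs if the t-tests and the GEE disagree.

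**The concern.** Three features act together.

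1. The pre-test precedes the intervention, so a difference there cannot be an effect of the chatbot. Yet it is listed among the outcomes of a between-group hypothesis that spans all three assessments, and no text says how such a difference would be read.
2. The week 1 and week 4 t-tests compare raw scores. Any part of a starting difference that persists goes straight into the comparison. Without stated randomisation, a systematic starting difference cannot be excluded.
3. The GEE could guard against this, but only if its group-by-time contrast is the quantity tested and only if it takes precedence. Table 1-1 lists group and time without their interaction, and item (4)a speaks of differences in scores rather than in improvement. A group main effect fits that description and carries the same starting difference.

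What is at stake is the effectiveness conclusion: a significant post-test t-test could be reported as support for chatbot education when the groups simply began at different levels. If the groups are in fact balanced, the raw t-test instead loses precision whenever pre-test and post-test are correlated.

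**Working it through.** **Inputs.** From the documents: significance level 0.05 (sidedness not stated; two-sided assumed), two groups, three assessments, three outcomes. The plan gives no sample size, SD, correlation or effect size, so it has no figure to reproduce. Assumed for illustration: n per arm from 20 to 100; starting difference b = 0.3 SD; within-person correlation ρ = 0.5 or 0.7; chatbot effect zero unless stated.

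**Two patterns for the starting difference.** Full persistence: both post-tests differ by b. Partial carry-over: they differ by ρb.

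**What each analysis picks up when there is no effect:**

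| Analysis | Error, full persistence | Error, partial carry-over | Variance factor |
|---|---|---|---|
| Raw post-test t-test | b | ρb | 1 |
| Change (group-by-time) contrast | 0 | −b(1−ρ) | 2(1−ρ) |
| ANCOVA on pre-test | b(1−ρ) | 0 | 1−ρ² |

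Rejection rates come from the non-central t distribution with non-centrality error × √(n/2) / √(variance factor), and 2n−2 degrees of freedom (2n−3 for ANCOVA).

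**Raw t-test, full persistence**
- n = 20: 0.3 × √10 = 0.949, rejects 15.2%
- n = 40: 0.3 × √20 = 1.342, rejects 26.3%
- n = 60: 0.3 × √30 = 1.643, rejects 37.1%
- n = 100: 0.3 × √50 = 2.121, rejects 56.0%

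**Raw t-test, partial carry-over, n = 40**
- ρ = 0.5: 0.15 × √20 = 0.671, rejects 10.2%
- ρ = 0.7: 0.21 × √20 = 0.939, rejects 15.3%

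**ANCOVA, n = 40**
- Full persistence, ρ = 0.5: 0.15 × √20 / √0.75 = 0.775, rejects 11.9%
- Full persistence, ρ = 0.7: 0.09 × √20 / √0.51 = 0.564, rejects 8.6%
- Partial carry-over: 5.0% and 4.7% by simulation (10,000 runs)

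**GEE, n = 40** (simulation, 60,000 runs, complete data, group, time and their interaction in the model, robust Wald z; ρ = 0.5 and 0.7)
- Group-by-time contrast, full persistence: 5.7% and 5.5%
- Group-by-time contrast, partial carry-over: 11.3% and 9.0%
- Group main effect averaged over three visits, full persistence: 38.8% and 33.6%. The closed form agrees: the variance factor is (1+2ρ)/3, so 0.3 × √20 / √0.667 = 1.643 and 0.3 × √20 / √0.8 = 1.5, or about 38% and 32% by normal approximation.

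A separate simulation at 30, 50 and 100 per arm, using a joint two-degree-of-freedom group-by-time test, gave 5% to 7% under full persistence. The raw t-test at those sizes rejects 21%, 32% and 56% by normal approximation.

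**Across the six post-test t-tests** (three outcomes, two post-tests; n = 40, ρ = 0.5, between-outcome correlation 0.4, full persistence), at least one is significant in about 69% of trials if all three outcomes start 0.3 SD apart and 49% if only one does. With no starting difference it is 23%, which is multiplicity alone.

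**Power when the groups are balanced** (true difference 0.5 SD, n = 40)
- Raw t-test: 0.5 × √20 = 2.236, 59.8%
- ANCOVA: 2.236 / √0.75 = 2.582, 72.2% (ρ = 0.5); 2.236 / √0.51 = 3.131, 87.1% (ρ = 0.7)
- Change contrast: 2.236 / √1, 59.8% (ρ = 0.5); 2.236 / √0.6 = 2.887, 81.4% (ρ = 0.7)

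**The case against.** **The plan already contains the right test.** A between-group difference in improvement, modelled with group and time, is the group-by-time contrast; a main effect would not answer hypothesis 1-1-3 as written. This is the natural reading and deserves credit. It does not settle the matter: the interaction is left to inference, item (4)a describes something looser, and even a correct GEE leaves 1-1-2, 2-1-2 and 3-1-2 as separate hypotheses with no rule placing them below it.

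**The t-test fits its hypothesis literally.** Those hypotheses say only that scores differ between groups, not that the chatbot caused it. True, but the stated objective is effectiveness, and nothing stops a significant t-test from being read that way.

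**The pre-test comparison is an ordinary comparability check.** Possibly. Item (2)a already covers continuous variables between groups, however, and Table 1-1 places the pre-test under the hypothesis without calling it a check.

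**Allocation may have been random.** If so, each post-test t-test keeps 5% error on average, the inflation above applies only given a chance imbalance, and the remaining loss is precision. An experimental design does not by itself establish randomisation.

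**The change contrast is not always better.** This stands. At ρ = 0.5 with partial carry-over it has the same absolute error (0.15 SD) and variance as the raw t-test: it rejects 11% against 10%, and its power is identical. There ANCOVA is the analysis that helps, which is why both should be shown.

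**Conclusion.** The point holds and should be fixed. The textual facts are clear: raw t-tests at each visit, the pre-test among the outcomes, no stated random allocation, no written interaction, and no ranking of the GEE. Following the plan as written, a starting difference alone can support a between-group hypothesis.

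The size of the harm is uncertain, because every numerical input except the 5% level is assumed. Under a 0.3 SD difference that persists in full, false support from one post-test t-test runs from 15% to 56% over 20 to 100 per arm; at 40 per arm it falls to 10% to 15% if the difference partly fades. The problem is not fatal, since the planned GEE can answer the question once its contrast and its priority are written down.

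**What to change.** - Take the pre-test out of the outcomes for 1-1-2, 2-1-2 and 3-1-2, and report pre-test scores by group descriptively.
- Make the GEE the between-group test. State a mean model with group, time and group × time, and name the group × time contrasts at week 1 and week 4 as the tests, reported as mean differences in change with 95% confidence intervals.
- Add ANCOVA of each post-test on group and pre-test score as a supporting analysis. Note that it reduces, but does not remove, a fully persisting starting difference, and commit to commenting if it and the GEE disagree.
- Label any raw post-test t-tests that are kept as descriptive.
- A sentence on how participants were allocated would help readers judge how likely a systematic starting difference is; the changes above do not depend on it.

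The cost is SAP wording only, since the pre-test is already a planned measurement. The trade-off is that the change contrast gains no precision over the raw t-test at ρ = 0.5, where 2(1−ρ) = 1, and is itself off by b(1−ρ) in size if the starting difference fades to ρb. Showing ANCOVA beside it covers that case.
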